5.3.2. Dose Adjustment of Exemestane (Group A Phase 1b)

Since there is no anticipated drug-drug interaction between GS-5829 and exemestane, the dose, route and schedule for administration of exemestane in Group A is provided in package insert included in [Appendix 8](#). Dose adjustment for GS-5829 is provided in Section [5.3.1](#).

5.3.3. Dose Adjustment of Fulvestrant

Since there is no anticipated drug-drug interaction between GS-5829 and fulvestrant, the dose, route and schedule for administration of fulvestrant in the Phase 1 portion and the Phase 2 portion is provided in package insert included in [Appendix 9](#). Dose adjustment for GS-5829 is provided in Section [5.3.1](#).

5.4. Prior and Concomitant Medications

Pre-/peri-menopausal subjects must have commenced treatment with goserelin or an alternative LHRH agonist at least 4 weeks prior to C1D1. If subjects have received an alternative LHRH agonist prior to study entry, they must switch to goserelin for the duration of the study on or before C1D1.

Subjects enrolling in the Phase 1b Dose Escalation portion of the study may have progressed on fulvestrant or exemestane.

Subjects enrolling in the Randomized Phase 2 Dose Expansion portion of the study may not have received prior fulvestrant.

In vitro data indicates GS-5829 is a substrate of CYP3A4. Co-administration of CYP3A4 inhibitors may increase GS-5829 exposure. As such, co-administration of moderate and strong CYP3A4 inhibitors with study drug is prohibited in this study. Co-administration of CYP3A4 inducers may decrease GS-5829 exposure. As such, moderate and potent CYP3A4 inducers are prohibited while subject is on study drug and within 2 weeks prior to study drug. Examples of moderate and strong CYP3A4 inhibitors and inducers are provided in the table below.

Table 5-3. Examples of Concomitant Medications Prohibited in this Study

	Moderate	Strong
CYP3A4 Inhibitor	aprepitant, ciprofloxacin, crizotinib, diltiazem, erythromycin, fluconazole, imatinib, verapamil	clarithromycin, conivaptan, grapefruit juice, itraconazole, ketoconazole, nefazodone, posaconazole, telithromycin, voriconazole
CYP3A4 Inducer	bosentan, modafinil, nafcillin	carbamazepine, phenytoin, rifampin, St. John's wort

Toxicology data from dogs demonstrated minimal to moderate gastrointestinal, pulmonary, muscular and intracardiac bleeding. The mechanism for the bleeding is not understood. Anticoagulant medications are prohibited on study. This includes vitamin K antagonists (e.g., warfarin), low molecular weight heparin, Factor Xa inhibitors, thrombin inhibitors and aspirin. If anticoagulation/antiplatelet therapy needs to be initiated while on study treatment, the investigator should consult with the Gilead medical monitor to determine if study treatment should be discontinued.

5.5. Accountability for GS-5829, Exemestane and Fulvestrant

The investigator is responsible for ensuring adequate accountability of all used and unused investigational medicinal products (IMP). This includes acknowledgement of receipt of each shipment of IMP (quantity and condition). All used and unused IMP dispensed to subjects must be returned to the site.

Study drug (GS-5829 and fulvestrant (only for sites outside of US)) accountability records will be provided to each study site to:

- Record the date received and quantity of study drug kits
- Record the date, subject number, subject initials, the study drug kit number dispensed
- Record the date, quantity of used and unused study drug returned, along with the initials of the person recording the information.

5.5.1. GS-5829, Exemestane (Group A Phase 1b) and Fulvestrant Investigational Medicinal Product Return or Disposal

Study drugs should be retrieved from each subject at the end of each dispensing interval. The quantity of study drug and the date returned by the subject should be recorded in the study drug accountability records. Whenever possible, study drug returned by the subject should be retained for review by the study site monitor prior to destruction.

For additional information about study drug accountability, return and disposal, refer to Section 9.1.7.

6. STUDY PROCEDURES

The study procedures to be conducted for each subject enrolled in the study are presented in tabular form in [Appendix 2](#) and described in the text that follows. Additional information is provided in the study procedures manual.

The investigator must document any deviation from protocol procedures and notify the sponsor or contract research organization (CRO).

Safety and tolerability assessments will include regular monitoring of AEs, changes from baseline in laboratory variables, physical examinations, vital signs, and special safety assessments like ECGs.

From the time of obtaining informed consent through the first administration of investigational medicinal product, record all serious adverse events (SAEs), as well as any non-serious AEs related to protocol-mandated procedures on the AEs electronic case report form (eCRF). All other untoward medical occurrences observed during the Screening period, including exacerbation or changes in medical history are to be captured on the medical history eCRF. See Section [7](#) for additional details.

6.1. Subject Enrollment and Treatment Assignment

[figure not shown]
Subjects will be assigned a unique screening number at the time of consent. Subject eligibility will be established at the conclusion of the screening evaluations. Once eligibility is confirmed, subjects will be assigned a unique subject number. The screening number and/or subject ID will be assigned for that individual subject by Gilead. The investigator will submit an enrollment form to Gilead and/or designee for review and approval prior to enrollment of the subject.

It is the responsibility of the investigator to ensure that each subject is eligible for the study before start of treatment.

6.2. Study Procedures Descriptions

6.2.1. Informed Consent

All subjects must sign and date the most recent Institutional Review Board (IRB)/Independent Ethics Committee (IEC) approved informed consent form before any study procedures are performed. PPD

Subjects who screen fail must re-sign the informed consent, in the event any screening procedures will be performed outside of the 28-day screening window from the time of the first informed consent.

6.2.2. Medical History

A complete medical history will be obtained by the investigator or qualified designee at screening and recorded on the eCRF. Medical history will include information on the subject's significant past medical events (e.g., prior hospitalizations or surgeries), a review of the disease under study, prior anti-cancer therapies, and any concurrent illnesses.

6.2.3. Prior and Concomitant Medications

All medications taken up to 30 days prior to the screening visit will be recorded on the eCRF. In addition, supportive therapies given during the course of the study (e.g. blood transfusion, growth factor) should be collected and recorded on the eCRF.

At each study visit, the site will capture any and all medications taken by the subject since the last visit or during the visit (as applicable). Concomitant medications include prescription and non-prescription medications, pre-infusion medications (e.g. anti-emetics), and vitamins and minerals.

6.2.4. Physical Examination

The investigator or qualified designee will perform a complete physical examination at designated time points during the study (Refer to [Appendix 2](#)). Pre-dose abnormal findings will be reported on the medical history page of the eCRF. Any changes from the pre-dose baseline physical examination that represent a clinically significant deterioration will be documented on the AE page of the eCRF. Screening and End of Treatment (EOT) physical examinations will be complete physical examinations. Beginning at C1D1, a modified physical examination will be performed to monitor for any changes, and will also include weight and assessment of disease-related clinical signs and symptoms.

Weight (without shoes) should be measured with each physical examination.

Height (without shoes) should be measured at screening only.

6.2.5. Vital Signs

Vital signs will include blood pressure, respiratory rate, pulse, and temperature. All measurements will be recorded on the appropriate eCRF page with appropriate source documentation. Any abnormal measurements may be repeated and reported as AEs if appropriate. All measures of blood pressure will be performed using standard sphygmomanometry. Measurements of blood pressure should be taken per institutional guidelines.

C1D1 vital signs will be taken within 15 min pre-GS-5829 dose and 2 and 4 hours post dose (+/- 15 min). At all subsequent visits, vital signs will be taken pre-GS-5829 dose only.

6.2.6. Electrocardiogram

12-lead electrocardiograms (ECGs) reporting ventricular rate, PR, QRS, QT, and QTc intervals will be obtained at the applicable study visits and transferred to a central vendor for storage.

Triplicate ECGs will be collected at any time during the Screening window, C1D1, Day 1 of Cycles 2-6 (at pre-dose), and at EOT. In the Phase 1b Dose Escalation phase of the study, triplicate ECGs will be collected on C1D1 at pre-dose and 1-4 hrs post-dose and on C1D15 at pre-dose, 1 hour, 2 hours, 3 hours, 4 hours, 6 hours, and 8 hours post dose (+/- 20 min). In the Randomized Phase 2 Dose Expansion phase of the study, triplicate ECGs will be collected on C1D1 at pre-dose and 1-4 hrs post-dose and on C1D15 at pre-dose, 1 hour, 2 hours, 4 hours, and 6 hours post dose (+/- 20 min).

ECGs should always be collected prior to pharmacokinetics (or any other blood draw) if they are to be collected at the same nominal time point. Subjects should be resting quietly and free of distraction (e.g., television, conversation) for 10 minutes prior to ECG collection and ECGs should be collected over a 5 minute window at each time point.

The investigator or qualified designee will review all ECGs. The ECG tracings will be maintained in the source documentation of each subject and the appropriate data reported on the eCRF.

6.2.7. Echocardiogram

Echocardiograms will be performed at the time points listed in the Study Procedures Table ([Appendix 2](#)). Multigated acquisition (MUGA) scans are also acceptable. However, the same modality must be used throughout study participation.

Abnormal echocardiogram findings that are considered clinically significant by the investigator should be reported as AEs and recorded in the AE eCRF if the finding meets the definition of an AE.

6.2.8. ECOG Performance Status

ECOG Performance Status is an investigator assessment of the impact of the disease on the subject's activities of daily living. ECOG assessments will be performed at the time points listed in the Study Procedures Table ([Appendix 2](#)). ECOG will be scored using the scale index in [Appendix 6](#).

6.2.9. Adverse Events

Subjects will be assessed for AEs per guidelines in the National Cancer Institute (NCI) CTCAE (version 4.03) at the time points outlined in [Appendix 4](#). Any AEs reported after informed consent is obtained and throughout the study will be recorded on the eCRF with appropriate source documentation. The subject will be assessed for AEs approximately 30 days after the last dose of study drug. Please refer to [Appendix 4](#) CTCAE grading criteria.

Please refer to Section [7](#) for additional information on AE reporting.

6.2.10. Disease Assessments

6.2.10.1. CT or MRI

Subjects will be assessed by CT scan with contrast (or MRI, if unable to tolerate CT contrast) of the chest, abdomen and pelvis to document metastatic disease, identify target lesions and to assess response as per RECIST 1.1 (refer to [Appendix 7](#)). The same assessment methods should be used for the subject throughout all treatment cycles. CT, or MRI scans will be obtained at the applicable study visits per the Study Procedures Table ([Appendix 2](#)) and transferred to a central vendor for storage.

In subjects who cannot tolerate iodinated contrast, a CT of the lung without contrast and MRI of the abdomen and pelvis should be performed. Imaging by CT scan (with contrast) or MRI or applicable scan will be performed at Screening (within 28 days before C1D1 if the scan was performed as part of standard medical practice) and every 8 weeks for the first year and then every 12 weeks during the treatment period regardless of cycle number or dose interruption. During the treatment, scans may be performed at time points other than 12 weeks, as clinically indicated, to assess tumor progression.

Tumor burden will be characterized at baseline and subsequent response assessments will be carried out according to the RECIST v. 1.1 (refer to [Appendix 7](#)). The same radiographic procedure and specification (e.g., the same contrast agent, slice thickness, etc.) used to define measurable lesions at baseline must be used throughout the study for each subject.

Subjects who discontinue study treatment for reasons other than disease progression will continue to have tumor assessments performed during the follow up visits every 8 weeks for the first year and then every 12 weeks until disease progression, initiation of new anti-cancer therapy, or discontinuation from the overall study participation (death, subject's request, lost to follow-up) whichever happens first. Every effort should be made to perform a last tumor assessment before starting a new anti-cancer therapy. Additional unscheduled tumor assessments may be performed as clinically indicated at any time.

6.2.10.2. Bone Scans

All subjects will undergo radionuclide bone scan at Screening (within 12 weeks prior to randomization). Bone scans performed before the signing of informed consent as routine procedures (but within 12 weeks before randomization) do not need to be repeated and may be

used as baseline assessments as long as (1) tests were performed using the method requirements outlined in RECIST v.1.1 (2) appropriately documentation indicating that these radiographic tumor assessments were performed as standard of care is available in the patient's source notes.

Any suspicious abnormalities (i.e., hotspots) identified on the bone scans at baseline and on subsequent bone scans MUST be confirmed by X-ray, CT scan with bone windows or MRI. The same modality must be used throughout the trial for confirmation for a given lesion/patient. Bone lesions identified at baseline will be followed up according to the same assessment schedule and every 8 weeks (± 7 days) for the first year and then every 12 weeks (± 7 days) from the date of C1D1 during the treatment period. Scans at the EOT visit are not necessary if the prior scan was performed within 4 weeks prior to the EOT visit date. Bone scans will be obtained at the applicable study visits per the Study Procedures Table ([Appendix 2](#)) and transferred to a central vendor for storage.

Bone lesions imaging:

- If bone lesions were identified at baseline as the only sites of a subject's disease the following assessment must be performed:
 - CT scan/MRI every 8 weeks (± 7 days) for the first year and then every 12 weeks (± 7 days) from the date of C1D1 and to confirm CR using the same modality used to confirm the bone lesions at baseline. Areas that have received palliative radiotherapy on study cannot be used to assess response to study treatment.
- If no bone lesions were identified at baseline, or if bone is not the only site of a subject's disease, bone scans will only be repeated as clinically indicated (i.e., subject describes new or worsening bone pain, or has increasing alkaline phosphatase level, or other signs and symptoms of new/progressing bone metastases) but are required to confirm CR. Abnormalities found on subsequent bone scans shall also be confirmed by X-ray, CT or MRI.

6.2.11. Laboratory Assessments

Screening laboratory samples should be obtained within 28 days prior to C1D1 dose (GS-5829). Local laboratory complete blood count (CBC) assessments may be collected as required for dose adjustments throughout the study. Local laboratory assessments resulting in a dose change will be reported on the eCRF.

The central laboratory will be responsible for chemistry, hematology, and coagulation testing per [Table 6-1](#) and storage of other study samples. If central laboratory results are not available, local laboratories may be used for dosing decision. Other tests listed in [Table 6-1](#) will be performed by Gilead or a designated laboratory. Any sample collected per the Study Procedures Table ([Appendix 2](#)) may be analyzed for any tests necessary to ensure subject safety. Specific instructions for processing, labeling, and shipping samples will be provided in the central laboratory manual. The date and time of sample collection will be recorded in the subject's source documentation and reported to the central laboratory.

The date and time of previous GS-5829 dose will be recorded in the subject's source documentation on days where pharmacokinetics is collected. WBC differentials will be reported as absolute counts. All laboratory tests must be reviewed for clinical significance by the investigator or qualified designee. Eligibility will be based on central laboratory assessments.

C1D1 pre-dose samples may be drawn up to 2 days prior to the visit.

The analytes listed in [Table 6-1](#) will be tested.

Table 6-1. Analytes

Serum Chemistry	Hematology	Other
Sodium	White Blood Cell (WBC) Count	Serum β-hCG for pregnancy test
Potassium	Hemoglobin	GS-5829 concentration
Chloride	Hematocrit	Concentrations of GS-5829
Glucose	Platelet Count	metabolite(s), fulvestrant, and/or
BUN	Neutrophils (ANC)	metabolites, as applicable, may be
Creatinine	Lymphocytes	determined
Creatinine Clearance ^a	Monocytes	PPD
ALT	Basophils	Hepatitis B surface antigen ^d
AST	Eosinophils	Hepatitis C antibody
Alkaline phosphatase	Coagulation	
Total bilirubin ^b	PT/INR ^c	FSH
Total protein	aPTT ^c	Serum Estradiol
Albumin		Hepatitis C RNA Reflex
Calcium		26-hydroxyvitamin D
Magnesium		HIV
Phosphate		Urine pregnancy test
AAG		
CRP		

a Cockcroft-Gault using Actual Body Weight: CRCL (mL/min) = [(140-age(years)) * weight(kg)] / (serum creatinine (mg/dL)*72)

b Includes direct bilirubin

c Collected at Screening and pre-dose of C1D1, C1D15, C2D1

d HCV RNA Reflex is required

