4.2. Inclusion Criteria

Subjects must meet all of the following inclusion criteria to be eligible for participation in this study:

- 1) ≥ 18 years of age, female
- 2) Histologically or cytologically confirmed breast cancer with evidence of metastatic or locally advanced disease not amenable to resection or radiation therapy with curative intent and who have progressed during treatment with at least one prior hormonal therapy
 - a) Phase 1b Dose Escalation - Subjects may have had unlimited prior hormonal therapy and a total of 2 prior chemotherapy regimens (adjuvant chemotherapy is considered 1 regimen). Subjects may have progressed on fulvestrant or exemestane
 - b) Randomized Phase 2 Dose Expansion - Subjects may have disease progression during treatment or within 12 month of completion of endocrine therapy (tamoxifen, and/or AI) in the adjuvant setting, or disease progression during treatment with endocrine therapy (tamoxifen, AI or CDK4/6 inhibitor plus AI) for advanced/metastatic disease. Subjects may have had unlimited prior hormonal therapy, but must be naïve to fulvestrant in the metastatic setting. A total of 2 prior chemotherapies are allowed, however, only one for metastatic disease is permitted.
- 3) Documentation of ER positive breast cancer ($\geq 1\%$ positive stained cells by local standards) based on the most recent tumor biopsy, unless bone-only disease
- 4) Documented HER2-negative tumor based on local testing on most recent tumor biopsy (immunohistochemistry score 0/1+ or negative by in situ hybridization HER2/CP17 ratio < 2 or for single probe assessment HER2 copy number < 4)

- 5) Post, pre or peri-menopausal subjects considered to be in the post-menopausal state as defined by one of the following:
 - a) Age \geq 60 years
 - b) Age $<$ 60 years and cessation of regular menses for at least 12 consecutive months in the absence of chemotherapy, tamoxifen, toremifene, or ovarian suppression and serum estradiol and follicle-stimulating hormone (FSH) level within the post-menopausal range
 - c) Prior bilateral oophorectomy
 - d) Pre-/peri-menopausal women can be enrolled if amenable to be treated with the luteinizing-hormone releasing hormone (LHRH) agonist goserelin. Subjects must have commenced treatment with goserelin or an alternative LHRH agonist at least 4 weeks prior to C1D1. If subjects have received an alternative LHRH agonist prior to study entry, they must switch to goserelin on or before C1D1 for the duration of the study

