- 6) Measurable disease defined per RECIST v. 1.1 or bone-only disease must have a lytic or mixed lytic blastic lesion that can be accurately assessed by CT or MRI. Subjects with bone-only disease and blastic-only metastases are not eligible
- 7) All acute toxic effects of any prior antitumor therapy resolved to Grade \leq 1 before the start of study drug dosing (with the exception of alopecia [Grade 1 or 2 permitted] and neurotoxicity [Grade 1 or 2 permitted])
- 8) Eastern Cooperative Oncology Group (ECOG) Performance Status of \leq 1
- 9) Life expectancy of \geq 3 months, in the opinion of the investigator
- 10) Adequate organ function defined as follows:
 - a) Hematologic: Platelets \geq 100 \times 10^9 /L; Hemoglobin \geq 9.0 g/dL; ANC \geq 1.5 \times 10^9 /L (without platelet transfusion or any granulocytic growth factors within previous 7 days of the hematologic laboratory values obtained at screening visit)
 - b) Hepatic: AST / ALT \leq 2.5 \times upper limit of normal (ULN) (if liver metastases are present, \leq 5 \times ULN); total or conjugated bilirubin \leq 1.5 \times ULN
 - c) Renal: Serum Creatinine \leq 1.5 \times ULN or creatinine clearance (CrCl) \geq 60 mL/min as calculated by the Cockroft-Gault method
- 11) Coagulation: International Normalized Ratio (INR) \leq 1.2
- 12) Negative serum pregnancy test ([Appendix 5](#))
- 13) Female subjects of childbearing potential who engage in heterosexual intercourse must agree to use protocol specified method(s) of contraception as described in [Appendix 5](#)

- 14) Females who are nursing must agree to discontinue nursing before C1D1
- 15) Able and willing to provide written informed consent to participate in the study

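### Table 6-1 prints the Cockcroft-Gault formula without a sex term in an all-female trial; with the conventional factor of 0.85, creatinine clearance as printed is about 18% too high

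*Protocol*

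**What the plan says.** Protocol Section 6.2.11 lists creatinine clearance among the serum chemistry analytes in Table 6-1. Footnote a gives the calculation: "Cockcroft-Gault using Actual Body Weight: CRCL (mL/min) = [(140-age(years)) * weight(kg)] / (serum creatinine (mg/dL)*72"). It contains no multiplier for sex.

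Inclusion criterion 1 (Section 4.2) reads "18 years of age, female", preceded by the at-least sign, so there are no men in the trial. Criterion 10c, which also appears in the synopsis, sets two renal alternatives joined by an or: serum creatinine up to 1.5 x "ULN or creatinine clearance (CrCl") of at least "60 mL/min as calculated by the Cockroft-Gault method". Section 6.2.11 adds: "Eligibility will be based on central laboratory assessments". The footnote is the only place in either document where the calculation is spelled out, and no female factor appears anywhere in the protocol or SAP.

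SAP 7.2.1 plans descriptive summaries of baseline, visit values and change for each protocol-specified laboratory test. SAP 4.3 counts enrolled subjects who failed an eligibility criterion. SAP Section 1 reports that the study was discontinued during dose escalation and that all subjects have stopped study drug and had their safety follow-up visit.

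**The concern.** Criterion 10c names a method and footnote a prints an equation under that name. For women, the method as conventionally defined includes a reducing factor, and the printed equation has none. A laboratory that follows the footnote literally would therefore report a clearance that is too high by the same proportion for every subject.

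Two uses are exposed. The first is eligibility: the clearance alternative matters only for women whose creatinine is already above 1.5 x ULN, and an inflated value could let one of them meet 10c when the named method would not. The second is reporting: if creatinine clearance is tabulated under SAP 7.2.1, levels and absolute changes would both be overstated, and the SAP 4.3 count could miss a subject who failed 10c.

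**Working it through.** **Inputs from the documents**
- Printed formula: CG = (140 - age) x weight / (72 x SCr) (Table 6-1, footnote a).
- Limit on the clearance alternative: 60 mL/min (criterion 10c).
- Population: all female (criterion 1).

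**Assumptions**
- Female factor f = 0.85, the conventional factor of the named method; range 0.80 to 0.90.
- ULN for serum creatinine: not stated in the documents; 0.9 to 1.2 mg/dL tried.

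The 60 mL/min is a threshold and not a derived figure, so there is nothing to reproduce first.

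**Size of the overstatement.** With the factor, clearance is f x CG, so the printed value is too high by 1/f - 1 whatever the age, weight or creatinine. A printed 60 corresponds to 60 x f. A factor-adjusted 60 would print as 60 / f.

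| f | Overstatement | Printed 60 corresponds to | Adjusted 60 prints as |
|---|---|---|---|
| 0.80 | 25.0% | 48 | 75.0 |
| 0.85 | 17.6% | 51 | 70.6 |
| 0.90 | 11.1% | 54 | 66.7 |

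**A case that changes status** (ULN assumed 0.9, so 1.5 x ULN = 1.35 mg/dL). Age 60, 80 kg, SCr 1.45: (80 x 80) / (72 x 1.45) = 61.3 as printed, and 0.85 x 61.3 = 52.1. Creatinine fails its own alternative, so the formula decides the case.

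**How narrow the window is.** The minimum weight to reach 60 mL/min is 60 x 72 x SCr / (140 - age) as printed, and that divided by 0.85 with the factor. At age 60, with SCr at 1.5 x ULN:

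| Assumed ULN (mg/dL) | SCr | Minimum weight as printed | Minimum weight with factor |
|---|---|---|---|
| 0.9 | 1.35 | 72.9 kg | 85.8 kg |
| 1.0 | 1.50 | 81.0 kg | 95.3 kg |
| 1.1 | 1.65 | 89.1 kg | 104.8 kg |
| 1.2 | 1.80 | 97.2 kg | 114.4 kg |

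Only women between the two weights change status, and only if their creatinine is already above 1.5 x ULN.

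**A case that does not depend on the formula** (ULN assumed 1.0). Age 75, 55 kg, SCr 1.4: (65 x 55) / (72 x 1.4) = 35.5 as printed, 30.1 with the factor. She meets 10c on creatinine alone either way.

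**The case against.** The strongest objection is that the documents do not contradict themselves in figures: 10c names a method, the footnote defines it, and 0.85 is found in neither document. That stands to the extent that 0.85 must be labelled an assumption and given a range. It does not remove the point. The protocol invokes the method by name, the printed equation carries no sex term in a trial of women only, and any factor below 1 gives the same direction of error.

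A reader might go further and infer that the trial's renal eligibility limit is really 51 mL/min. The documents do not support that. Criterion 10c is an or, so neither 60 nor 51 is an overall floor, as the last worked case shows.

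A reader might also infer that every clearance in the database is wrong. That holds only if the central laboratory applied the footnote as printed, which the documents instruct but do not show.

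It is also fair to say that the consequences are small. Serum creatinine is a separate analyte and is unaffected. A constant multiplier leaves percentage change and ranking unchanged. The DLT definition, the GS-5829 dose-adjustment text and the efficacy endpoints do not use creatinine clearance, and SAP Section 3 plans no formal testing. All of this stands and limits the point to reported clearance values and the 10c check. Finally, with the study stopped, changing the formula can no longer alter who is enrolled; that shapes the fix below.

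**Conclusion.** The point holds in a limited form. The footnote omits a sex term although all subjects are women. Assuming the conventional factor of 0.85, clearance calculated as printed is about 18% too high (11% to 25% for factors of 0.90 to 0.80). Within the clearance alternative of 10c, a printed 60 mL/min corresponds to about 51 mL/min (48 to 54).

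The eligibility effect is confined to women with serum creatinine above 1.5 x ULN and is likely to touch few subjects, if any. Sample size, power and PFS are not affected. What remains is the accuracy of any creatinine clearance reported in the final analysis and of the eligibility-deviation count. The conclusion rests on the assumed factor and on the laboratory having followed the footnote; the weight bands rest also on the assumed ULN.

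**What to change.** Correct footnote a so that it matches the method named in 10c by adding the female factor, or state that the uncorrected value was intended and reconcile it with 10c in both the synopsis and Section 4.2. Which renal limit is right is for the sponsor to decide.

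Since enrolment and treatment are over, carry the decision into the final analysis:
- Ask the central laboratory which formula it used.
- If it used the printed one and the factor applies, recompute creatinine clearance for the SAP 7.2.1 summaries. At f = 0.85 this is an exact rescaling by 0.85 that needs no new data.
- Recheck 10c for the SAP 4.3 summary. At f = 0.85 only subjects with screening creatinine above 1.5 x ULN and a printed clearance from 60 to below 70.6 mL/min need review.
- Record the change in the clinical study report, as SAP Section 1 requires for changes after finalization, and do not carry the footnote into other protocols.

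The cost is one protocol line and one recalculated laboratory field. The downside is that a few subjects may be reclassified as not meeting 10c.
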